### **6.2. Secondary Efficacy Analyses**

#### **6.2.1. Definition of Secondary Efficacy Endpoints**

Secondary efficacy endpoints include the following:

- Change from baseline in plasma  $\log_{10}$  HIV-1 RNA at postbaseline visits
- Proportion of subjects with plasma HIV-1 RNA  $\geq 50$  copies/mL at any postdose timepoint (up to 10 days after each dose for Cohorts 1-3 and 7 days after each dose for Cohorts 4-6)

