 - If ARV regimen is changed ≥ 45 days prior to Pre-Baseline/Day -13, plasma HIV-1 RNA < 50 copies/mL at Pre-baseline/Day -13 visit is required.
- No documented history of resistance to any components of the current ARV regimen
- Availability of a fully active alternative ARV regimen, in the opinion of the Investigator, in the event of discontinuation of the current ARV regimen with development of resistance.
- Hgb ≥ 11.5 g/dL (males) or ≥ 11 g/dL (females)
- WBC ≥ 4000 cells/ μ L
- Platelets $\geq 150,000$ /mL
- ANC ≥ 1500 cells/ μ L
- CD4 count ≥ 400 cells/ μ L
- Albumin ≥ 3.9 g/dL
- ALT and AST $\leq 2 \times$ ULN
- Estimated glomerular filtration rate ≥ 60 mL/min
- No autoimmune disease (e.g. lupus erythematosus, rheumatoid arthritis, inflammatory bowel disease, sarcoidosis, moderate or severe psoriasis)
- No evidence of current HBV infection
 - Positive anti-HBs antibody and negative HBsAg results are acceptable

- No evidence of current HCV infection
 - Positive anti-HCV antibody and negative HCV PCR results are acceptable
- No documented history of pre-ART CD4 nadir < 200 cells/μL
 - Unknown pre-ART CD4 nadir is acceptable
- No history of Class C AIDS-Defining Condition
 - No acute febrile illness within 35 days prior to Pre-Baseline/Day -13

Study Visits and
Procedures:

Visit Schedule:

The main study phase consists of a screening period of up to 35 days, a pre-treatment period of 14 Days (from Day -13 to Day 1), treatment period of 71 days (Cohorts 1 to 3), 127 days (Cohorts 4 to 6), CCI and a follow-up period of 30 days after the last dose of study drug is taken. Enrolled subjects will undergo the following scheduled study visits:

Cohort 1 to Cohort 3

Day -13 (**Pre-Baseline**)

Day 1 (**Baseline/Dose 1**), Day 3, Day 5, Day 8, Day 11

Day 15 (**Dose 2**), Day 17, Day 19, Day 22, Day 25

Day 29 (**Dose 3**), Day 31, Day 33, Day 36, Day 39

Day 43 (**Dose 4**), Day 45, Day 47, Day 50, Day 53

Day 57 (**Dose 5**), Day 59, Day 61, Day 64, Day 67

Day 71 (**Dose 6**), Day 73, Day 75, Day 78, Day 81

Day 101 (**End of Study**)

Cohort 4

Day -13 (**Pre-Baseline**)

Day 1 (**Baseline/Dose 1**), Day 2, Day 3, Day 8

Day 15 (**Dose 2**), Day 22

Day 29 (**Dose 3**), Day 36

Day 43 (**Dose 4**), Day 50

Day 57 (**Dose 5**), Day 58, Day 59, Day 64

Day 71 (**Dose 6**), Day 78

Day 85 (**Dose 7**), Day 92

Day 99 (**Dose 8**), Day 106
Day 113 (**Dose 9**), Day 120
Day 127 (**Dose 10**), Day 128, Day 129, Day 134
Day 157 (**End of Study**)

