Cohorts 5 to 9

Day -13 (**Pre-Baseline**)
Day 1 (**Baseline/Dose 1**), Day 2, Day 3, Day 8
Day 15 (**Dose 2**), Day 22
Day 29 (**Dose 3**), Day 31, Day 36
Day 43 (**Dose 4**), Day 45, Day 50
Day 57 (**Dose 5**), Day 58, Day 59, Day 64
Day 71 (**Dose 6**), Day 73, Day 78
Day 85 (**Dose 7**), Day 87, Day 92
Day 99 (**Dose 8**), Day 101, Day 106
Day 113 (**Dose 9**), Day 115, Day 120
Day 127 (**Dose 10**), Day 128, Day 129, Day 134
Day 157 (**End of Study**)

Subjects who prematurely discontinue study drug will be required to complete an Early Study Drug Discontinuation Visit within 30 days after their last dose of study treatment.

The Pre-Baseline/Day -13 visit has an allowable window of ± 3 days.

- Visits scheduled for 2, 4, 7, or 10 days after a Dosing visit, **except for Day 2, 3, 58, 59, 128 and 129** have an allowable window of ± 1 day.

The Day 101 and 157 visits have an allowable window of ± 3 days.

Non-dosing visits may occur at the investigator site or at other location agreed by the subject and mobile nurse vendor.

Screening Procedures:

Screening procedures include: complete physical examination, vital signs, height, weight, medical history (including route and estimated duration of HIV infection, pre-ART viral set point, and complete ARV history), HIV-1 RNA, ARV trough PK, hematology, serum chemistry, serum pregnancy test, urinalysis, HBV and HCV serologies, eGFR, and electrocardiogram (ECG). Pre-ART CD4 nadir and historical genotype will be collected if available.

In order to establish eligibility, Investigators may repeat screening procedures or laboratory assessments for subjects who have an acute illness or abnormal laboratory value that is expected to resolve without sequelae within the screening window.

On-Study Procedures:

Dosing:

For **Cohorts 1 to 3**, dosing visits will occur at Day 1, Day 15, Day 29, Day 43, Day 57, and Day 71. For **Cohorts 4 to 9**, dosing visits will occur at Day 1, Day 15, Day 29, Day 43, Day 57, Day 71, Day 85, Day 99, Day 113 and Day 127. CCI

For **Cohorts 1 to 4**, subjects will fast for at least 2 hours before dosing. For **Cohorts 5 to 8**, subjects will fast overnight (at least 8 hours) before dosing. CCI

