Whole blood ISG mRNA panel: **For Cohorts 1 to 3**, immediately before and 2 days and 7 days after each dose of study drug, and at the end of the study (Day 101). **For Cohorts 4 to 9**, immediately before and 1 day, 2 days and 7 days after doses 1, 4 (only if Cohort 6 subjects receive 12 mg starting at Dose 4), 5 and 10. CCI

TLR7 genotyping: at Pre-Baseline/Day -13

Virology:

Plasma HIV-1 RNA: at every visit except Pre-Baseline (Day -13).

Cell-associated HIV-1 RNA/DNA (CAVR/CAVD), and plasma HIV-1 RNA by Single Copy Assay (SCA) will be collected immediately before and two days post Doses 1, 4, 6 and at end of the study (Cohort 1 to 3); immediately before and two days post Doses 1, 5, 10 and at end of the study (Cohorts 4 to 9). CCI

HIV-1 reservoir measurements: at Pre-Baseline/Day -13 and at the end of the study (Cohorts 4 to 9). CCI

Immunology:

Peripheral blood immune cell numbers for T/B/NK/pDC/mDC including: CD4 and CD8 populations, CD4/CD8 ratio, CD4% and lymphocyte activation (T, B and NK cells) by flow cytometry will be collected immediately before and two days post Doses 1, 3, and 6 (Cohorts 1 to 3), and immediately before, one and two days post Doses 1, 5 and 10 (Cohorts 4 to 9). CCI

FoxP3+ Treg cells by flow cytometry will be collected immediately before Doses 1, 3, and 6 (Cohorts 1 to 3), and immediately before Doses 1, 5 and 10 (Cohort 4 to 9). CCI

Changes in the levels of antiviral cytokines and inflammatory markers by chemiluminescence: immediately before and 2 days and 7 days after each dose, and at the end of the study (Cohorts 1 to 3). For subjects in Cohorts 4 to 9, immediately before, post dose days 1, 2 and 7 after Doses 1, 4 (only if Cohort 6 subjects receive 12 mg at Dose 4), 5 and 10. CCI

PBMC Intracellular cytokine staining (ICS) for Treg cells: immediately before and 2 days after Doses 1 and 6 for subjects in Cohorts 1 to 3.

HIV-specific T-cell responses by ELISPOT will be collected at Pre-Baseline/Day -13, immediately before Dose 6 and at the end of study for subjects in **Cohorts 1 to 3**.

For subjects in Cohorts 4 to 9, HIV-specific polyfunctional T cell Intracellular Cytokine Staining (ICS) and HIV-specific T-cell responses by ELISPOT will be collected at Pre-Baseline/Day -13 and at the end of the study. **CCI**

Stool sample will be obtained for microbiome analysis. (Day 1 and Day 157 for **Cohorts 5 to 9**). **CCI**

CCI

Additional End of Study Procedures:

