4.2. Inclusion Criteria (All Cohorts)

Subjects must meet all of the following inclusion criteria to be eligible for participation in this study.

- 1) The ability to understand and sign a written informed consent form, which must be obtained prior to initiation of study procedures
- 2) HIV-1 infected males and non-pregnant, non-lactating females ≥ 18 years at Pre-Baseline/Day -13
- 3) On antiretroviral (ARV) regimen for ≥ 12 consecutive months prior to Pre-Baseline/Day -13
 - a) The following agents are allowed as part of the current ARV regimen: NRTIs, raltegravir, dolutegravir, rilpivirine, and maraviroc
 - b) The following agents are NOT allowed as part of the current ARV regimen: HIV protease inhibitors (including low dose ritonavir), cobicistat-containing regimens, elvitegravir, efavirenz, etravirine, and nevirapine
 - c) A change in ARV regimen ≥ 45 days prior to Baseline/Day 1 for reasons other than virologic failure (e.g. tolerability, simplification, drug-drug interaction profile) is allowed
- 4) Plasma HIV-1 RNA levels < 50 copies/mL at screening
- 5) Documented plasma HIV-1 RNA levels < 50 copies/mL (according to the local assay being used) for ≥ 12 months preceding the screening visit (measured at least twice using a licensed assay with a lower limit of quantitation of at least 40 copies/mL)
 - a) Unconfirmed virologic elevations of ≥ 50 copies/mL (transient detectable viremia, or “blip”) prior to screening are acceptable. (If the lower limit of detection of the local HIV-1 RNA assay is < 50 copies/mL, the plasma HIV-1 RNA level cannot exceed 50 copies/mL on two consecutive HIV-1 RNA tests)
 - b) If ARV regimen is changed ≥ 45 days prior to Pre-Baseline/Day -13, plasma HIV-1 RNA < 50 copies/mL at Pre-baseline/Day -13 visit is required.
- 6) No documented history of resistance to any components of the current ARV regimen

- 7) Availability of a fully active alternative ARV regimen, in the opinion of the Investigator, in the event of discontinuation of the current ARV regimen with development of resistance
- 8) Hemoglobin ≥ 11.5 g/dL (males) or ≥ 11 g/dL (females)
- 9) White blood cell ≥ 4000 cells/ μ L
- 10) Platelets $\geq 150,000$ /mL
- 11) Absolute Neutrophil Count ≥ 1500 cells/ μ L
- 12) CD4 count ≥ 400 cells/ μ L
- 13) Albumin ≥ 3.9 g/dL
- 14) Alanine aminotransferase (ALT) and aspartate aminotransferase (AST) $\leq 2 \times$ upper limit of normal (ULN)

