8.1.3. Secondary Endpoint

The secondary endpoints are:

- Change from baseline in plasma HIV-1 RNA at post-baseline visits
- Proportion of subjects with plasma HIV-1 RNA > 50 copies/mL at any post-dose timepoint

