### 5.2. Baseline Disease Characteristics

The following baseline disease characteristics will be summarized:

- HIV-1 RNA ( $\log_{10}$  copies/mL)
- HIV-1 RNA categories (copies/mL) (a)  $< 50$  and (b)  $\geq 50$
- CD4 cell count (/ $\mu\text{L}$ )
- CD4+ cell count categories (/ $\mu\text{L}$ ): (a)  $< 50$ , (b)  $\geq 50$  to  $< 200$ , (c)  $\geq 200$  to  $< 350$ , (d)  $\geq 350$  to  $< 500$ , and (e)  $\geq 500$
- CD4 percentage (%)
- eGFRCG (mL/min)
- Mode of infection (HIV risk factors)
- HIV disease status
- Duration of being diagnosed with HIV disease (in years)
- Duration of ARV prior to study (in years)
- Pre-ARV HIV-RNA viral set point ( $\log_{10}$  copies/mL)
- Pre-ARV HIV-RNA categories (copies/mL): (a)  $\leq 100,000$ , (b)  $> 100,000$  to  $\leq 400,000$ , and (c)  $> 400,000$
- Pre-ARV CD4 cell count (/ $\mu\text{L}$ )
- Pre-ARV CD4 cell count categories (/ $\mu\text{L}$ ): (a)  $< 50$ , (b)  $\geq 50$  to  $< 200$ , (c)  $\geq 200$  to  $< 350$ , (d)  $\geq 350$  to  $< 500$ , and (e)  $\geq 500$

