#### **6.1.3. Analysis of Primary Efficacy Endpoint**

The maximum change from baseline in plasma  $\log_{10}$  HIV-1 RNA at any postdose timepoint up to Day 81 for Cohorts 1-3 or Day 134 for Cohorts 4-6 will be calculated for all subjects in the full analysis set using available on-treatment HIV-1 RNA data up to Day 81 for Cohorts 1-3 or Day 134 for Cohorts 4-6, and summarized by treatment group using descriptive statistics (n, mean, SD, 95% CI, median, Q1, Q3, minimum, and maximum).

The primary efficacy endpoint will be compared between each active treatment group and the pooled placebo group using a Wilcoxon rank sum test at a two-sided 0.05 significant level.

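### The SAP limits the protocol's any-post-dose viremia endpoint to 7 or 10 days after each dose and changes its threshold sign without giving a reason, and neither document conditions the endpoint on baseline

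*SAP*

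**What the plan says.** Protocol 8.1.3 defines the endpoint as "Proportion of subjects with plasma HIV-1 RNA > 50 copies/mL at any post-dose timepoint". Protocol 3.1 and 8.5.2 say the same. None of the three sets a time limit.

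SAP 6.2.1 changes the sign from above 50 to 50 or more, and counts samples only "up to 10 days after each dose for Cohorts 1-3 and 7 days after each dose for Cohorts 4-6". SAP 6.2.2 repeats this and compares each active group with pooled placebo by Fisher's exact test at a two-sided 0.05 level. No reason is given. The SAP's statement on changes from the protocol (7.7) covers safety analyses only, and its revision table is empty.

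The SAP primary endpoint (6.1.3) is the maximum change "using available on-treatment HIV-1 RNA data up to Day 81 for Cohorts 1-3 or Day 134 for Cohorts 4-6". It has no per-dose limit.

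The protocol synopsis schedules plasma HIV-1 RNA at every visit except Day -13. "Visits scheduled for 2, 4, 7, or 10 days after a Dosing visit" have a tolerance of one day either side, except a few named visits that do not include the +7 or +10 visits. SAP 3.8.2 uses nominal visits for by-visit summaries and has no rule for a window counted in days after a dose.

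On entry, Protocol 4.2 requires "Plasma HIV-1 RNA levels < 50 copies/mL at screening" and a documented history of suppression. It requires a value below 50 at Day -13 only after a change of regimen. It has no general Day 1 criterion.

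**The concern.** This responder proportion is a direct readout of whether the drug provokes detectable viremia. The two documents define it differently, and the difference could change who is a responder.

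- A rise seen only in the sample taken 14 days after a dose appears to count in the primary endpoint but does not count here.
- The window ends exactly on the nominal day of visits that may take place a day later.
- Neither definition separates a new rise from viremia that was already there. A subject at 60 copies/mL before the first dose and 55 on Day 3 would be a responder although the value fell.

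Groups are small, so a single reclassified active subject moves that group's rate by 1/6 = 16.7 percentage points.

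**Working it through.** The plan gives no power or event figure for this endpoint, so there is nothing of its own to reproduce. The check is a count of scheduled samples.

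**Inputs.** Visit days come from the synopsis visit schedule. Cohorts 1-3 have, after Dose 1, "Day 3, Day 5, Day 8, Day 11", and the same +2, +4, +7, +10 pattern after each of six doses. Cohorts 4-6 have ten doses, 14 days apart. Group sizes come from SAP 1.2 and 3.2: 6 active per cohort and 6 × 2 = 12 pooled placebo.

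**Step 1: samples outside the window.** Each post-baseline sample is given its days since the previous dose. A dosing-day sample is counted from the dose before it, because the procedure lists place dosing after the blood draws. A sample is outside if this exceeds 10 (Cohorts 1-3) or 7 (Cohorts 4-6).

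| Cohorts | Scheduled | Inside | Outside | Share outside | Share outside if dosing-day draws are read as pre-dose |
|---|---|---|---|---|---|
| 1-3 | 30 | 24 | 6 (Days 15, 29, 43, 57, 71, 101) | 6/30 = 20.0% | 1/25 = 4.0% |
| 4 | 26 | 16 | 10 (nine dosing days, Day 157) | 10/26 = 38.5% | 1/17 = 5.9% |
| 5-6 | 32 | 22 | 10 (nine dosing days, Day 157) | 10/32 = 31.3% | 1/23 = 4.3% |

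The last column removes the dosing-day draws (5, 9 and 9) from the denominator, leaving End of Study as the only loss.

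**Step 2: mismatch with the primary endpoint.** Days 81 and 134 are the last +10 and +7 visits (71 + 10; 127 + 7), so both endpoints stop at the same visit. Up to that visit they differ only in the dosing-day draws: 5/29 = 17.2%, 9/25 = 36.0% and 9/31 = 29.0% of samples.

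**Step 3: visits on the cut-off.** The +10 or +7 visit makes up 6/24 = 25.0%, 10/16 = 62.5% and 10/22 = 45.5% of in-window samples. In Cohort 4 it is the only in-window sample after 7 of 10 doses (all but Doses 1, 5 and 10). With nominal visits, none of these is lost. As an extreme bound, if actual days applied and every one of these visits were a day late, the totals outside would be 12/30 = 40.0%, 20/26 = 76.9% and 20/32 = 62.5%.

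**Step 4: sensitivity of the test.** For a of 6 active and b of 12 placebo responders, the probability of a table is C(6,a) × C(12,b) / C(18,a+b). The two-sided p sums the tables that are no more likely than the one observed.

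- 3/6 against 0/12: 20/816 = 0.025
- 2/6 against 0/12: 15/153 = 0.098
- 3/6 against 1/12: (240 + 15)/3060 = 0.083

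Moving one subject in either arm takes 0.025 above 0.05.

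**The case against.** The window has a plausible rationale. Protocol 1.1 and 1.3 report animal viremia within 24-72 hours of dosing, and Protocol 1.4 says the two-week interval is there to verify that viremia has resolved before the next dose. The limits coincide with the last non-dosing visit after each dose. This stands as a reason the sponsor could give, but the SAP does not give it.

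The larger loss depends on how dosing-day draws are read; as pre-dose, it is 4-6%. That also stands. The wider reading is favoured because the SAP primary uses the same any-postdose wording with no per-dose limit, and because the stated purpose of the interval makes the +14 sample informative about the preceding dose.

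Late rises are not lost to the trial. They appear to enter the primary endpoint, and they appear in the by-visit changes and the listings. Reverting to any post-dose sample would also leave sampling unequal across cohorts (30, 26 and 32), and would run past the primary's Day 81 or Day 134 limit by one sample per subject. The study is exploratory and unpowered, and SAP section 6 asks for caution with its unadjusted p-values. These points limit the weight of the concern, but they do not explain the change of definition.

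A reader might infer more, in four ways the documents do not support:

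- **That the SAP introduced the counting of pre-existing viremia.** The protocol endpoint has no baseline condition either.
- **That the baseline row for 50 or more in SAP 5.2 shows such subjects are expected.** The same list has CD4 rows below 350 although entry requires at least 400, so these look like template rows.
- **That draws at +8 or +11 will be lost.** This happens only if actual days are used.
- **That interim results prompted the change.** SAP 2.1.2 records that selected sponsor staff were unblinded to interim virology, but nothing links that to this definition. It only makes a documented reason more useful.

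**Conclusion.** The point holds as an undocumented departure from the protocol endpoint. The effect on scheduled samples is 20%, 38% and 31% (Cohorts 1-3, 4, 5-6) if +14 draws count as post-dose, and 4-6% if they do not. These are shares of samples, not changes in the responder rate. The sign change affects only a value of exactly 50.

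The boundary problem is an ambiguity and a risk, not a certain loss.

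The missing baseline condition is a separate gap shared by both documents. A subject starting at 50 or more is miscounted only if an eligible post-dose value is also 50 or more without a rise. The documents give no rate for this, so its frequency is unknown.

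The change should be made because it is cheap and one subject can decide a comparison at the stated level. The exploratory design makes it no more than that.

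**What to change.** In SAP 6.2.1 and 6.2.2:

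1. Report the protocol-defined endpoint, counting any post-dose sample, with one threshold sign used in both documents. State that dosing-day draws after Day 1 count as post-dose, and that End of Study is included. Keep the 7/10-day version as supportive and give its reason.
2. Define that window by nominal visit (+7 or +10), so that an on-protocol draw at +8 or +11 is included.
3. Add a responder analysis restricted to subjects with baseline below 50, and list subjects with baseline of 50 or more separately.

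The cost is SAP wording, minor programming and one or two extra tables; no new data are needed. The baseline-restricted analysis may have a slightly smaller denominator, while the full analysis set is kept for the main version.

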### **6.2.2. Analysis of Secondary Efficacy Endpoints**

The full analysis set will be used for secondary efficacy endpoint analysis.

Baseline and change from baseline in plasma  $\log_{10}$  HIV-1 RNA at postbaseline visits will be summarized by treatment group using descriptive statistics. The change from baseline in plasma  $\log_{10}$  HIV-1 RNA at postbaseline visits will be analyzed in the same fashion as that of the primary efficacy endpoint.

The number and proportion of subjects with plasma HIV-1 RNA  $\geq 50$  copies/mL at any postdose timepoint (up to 10 days after each dose for Cohorts 1-3 and 7 days after each dose for Cohorts 4-6) will be summarized by treatment group and compared between each active treatment group and the pooled placebo group using a Fisher's exact test at a two-sided 0.05 significant level. The number and percentage of subjects with HIV-1 RNA in the following categories will be summarized:

- $\geq 50$  copies/mL
- $< 50$  copies/mL

### **6.3. Other Efficacy Analyses**

#### **6.3.1. Definition of the Other Efficacy Endpoints**

Other efficacy endpoints include the following:

- Change, percentage change and fold change from baseline in the levels of serum cytokines (including IFN- $\alpha$ , IL-1RA, IP-10, and ITAC)
- Fold change in mRNA for ISGs including MX1, OAS1 and ISG15
- Change and percentage change from baseline in CD4/CD38/HLADR, CD8/CD38/HLADR and NK cell activation

#### **6.3.2. Analysis of Other Efficacy Endpoints**

The full analysis set will be used for other efficacy endpoint analysis.

Change percentage change and fold change from baseline (postbaseline/baseline) in the levels of serum cytokines will be summarized by treatment group using descriptive statistics and compared between each active treatment group and the pooled placebo group using a Wilcoxon rank sum test at a two-sided 0.05 significant level.

Fold change from baseline (postbaseline/baseline) in mRNA for ISGs will be analyzed similarly as above.

Change and percentage change from baseline in CD4/CD38/HLADR, CD8/CD38/HLADR and NK cell activation will also be analyzed similarly as above.

## **7. SAFETY ANALYSES**

### **7.1. Adverse Events and Deaths**

#### **7.1.1. Adverse Event Dictionary**

Clinical and laboratory adverse events (AEs) will be coded using the current version of MedDRA. System organ class (SOC), high-level group term (HLGT), high-level term (HLT), preferred term (PT), and lower-level term (LLT) will be provided in the AE dataset.

#### **7.1.2. Adverse Event Severity**

Adverse events are graded by the investigator as Grade 1 (mild), Grade 2 (moderate), Grade 3 (severe), or Grade 4 (life threatening) according to toxicity criteria specified in the protocol. The severity grade of events for which the investigator did not record severity will be categorized as “missing” for tabular summaries and data listings. The missing category will be listed last in summary presentation.

#### **7.1.3. Relationship of Adverse Events to Study Drug**

Study drug related AEs are those for which the investigator selected “Related” on the AE CRF to the question of “Related to Study Treatment.” Relatedness will always default to the investigator’s choice, not that of the medical monitor. Events for which the investigator did not record relationship to study drug will be considered related to study drug for summary purposes. However, by-subject data listings will show the relationship as missing.

